## 3. Consolidation

Patients in CR or CRi can continue with up to 6 consolidation cycles.

- Clofarabine 15 mg/m² IV daily over approximately 60 minutes for 3 days on days
   1 3 (for 2 days on days 1-2 in patients 61 80 years of age or with PS 2 or 3)
- Idarubicin 6 mg/m² IV over 30 60 minutes daily for 2 days on days 1 2 (3
   mg/m² for 2 days on days 1-2 in patients 61-80 years of age or with PS 2 or 3)
  - To start 1 2 hours after the clofarabine
- Cytarabine 1,000 mg/m² IV over approximately 2 hours daily for 3 days on days
   1 3 (for 2 days on days 1-2 in patients 61 80 years of age or with PS 2 or 3)
  - To start 3 6 hours after the clofarabine
- Vincristine 2 mg (FLAT dose) IV over 15 30 minutes on days 1, 8, and 15
- Dexamethasone 40 mg IV daily for 4 days on days 1 4 and days 15 18
  - May be given 30 60 minutes prior to each dose of cytarabine during consolidation on days 1 – 3 (if rituximab given, can administer dexamethasone prior to rituximab on day 1)

For patients with CD20 positive disease ( $\geq$  10% of the lymphoid population), rituximab may be added to the regimen as follows during consolidation cycles 1 – 3:

• Rituximab 375 mg/m² IV infused according to package labeling on days 1 and 8

Rituximab will be infused according to the package insert. Premedications
will be administered according to departmental standard/prescribing
information to prevent infusion related reactions.

The doses and schedule can be modified for the following situations:

- For patients 61 80 years of age or with performance status of 2 or 3: give clofarabine and cytarabine for 2 days; give idarubicin 3 mg/m² for 2 days as mentioned above.
- Further dose reductions can be considered after discussion with the PI

Cycles may be repeated every 3 to 10 weeks based on leukemia response and resolution of clinically significant drug-related toxicities. Prior to each consolidation cycle, the ANC should be  $\geq 1.0 \times 10^9$ /L, and the platelet count should be  $\geq 60 \times 10^9$ /L (except for patients who are considered to have achieved a CRp following induction/reinduction and in whom the platelet count may be lower). Patients with borderline values for ANC and platelet count (value up to 10% lower than recommended) can still proceed with the next consolidation cycle if this is judged to be in the best interest of the patients and after discussion with the principal investigator and the discussion documented in the patient's medical record. In addition, any clinically significant drug-related non-hematologic toxicity experienced by the patient must return to  $\leq$  grade 2 before receiving the next cycle. Doses missed or held during a cycle of treatment will not be made up and are recorded as being omitted. If patients experience multiple study drug-

related toxicities or experience significant infections, dose adjustments may need to be made based on the most severe toxicity and based on the drug causing the toxicity.

#### 4. Dose Modifications

Drug doses in subsequent consolidation cycles may be modified for clinically significant drug-related > grade 2 non-hematologic toxicities. Dose reductions can also be made in other clinical situations where this step is considered to be in the best interest for the patient and after discussion with the principal investigator and the discussion documented in the patient's medical record. Doses of each individual drug can be modified if a toxicity is considered due this particular drug.

The following are suggestions for dose modifications in subsequent treatment courses:

- Persistent neutropenia (< 1,000) or thrombocytopenia (< 50,000) greater than 42 days from previous cycle: reduce doses of clofarabine, cytarabine and idarubicin by 20 25%

- Clinically significant peripheral neuropathy persisting for > 2 weeks:
  - 50% reduction of vincristine (1 mg) for Grade 2 persistent neuropathy
  - Eliminate vincristine for Grade 3-4 neuropathy, seizures and Ileus suspected to be related to vincristine

Organ specific dose adjustments:

	Cytarabine	Idarubicin	Clofarabine	Vincristine
Serum Creatinine (mg/dL)				
2.1 – 3	75% of current dose	75% of current dose	75% of current dose	100% of current dose
Above 3	Discuss with PI			
Bilirubin (mg/dL)				
2 – 3	100% of current dose	75% of current dose	100% of current dose	50% of current dose or omit
3.1 – 5	100% of current dose	50% of current dose	Discuss with PI	Omit
Above 5	100% of current dose	Omit	Discuss with PI	Omit

# 5. Targeted therapy

Approximately a third of patients with AML may harbor activating FLT3-ITD mutations; such mutations are also observed in patients with biphenotypic or mixed lineage leukemias. We have previously shown that combining sorafenib with chemotherapy in patients with FLT3-ITD mutations is both safe and efficacious. (Ravandi et. al. JCO 2010). Therefore, patients with known FLT3-ITD mutations will be allowed to receive sorafenib therapy at a dose of 400mg orally twice daily on days 1-14 during induction

and then continuously for 28 days per cycle starting with cycle 2, at the discretion of the treating physician. Dose adjustments and interruptions of the sorafenib are per standard of care and at the discretion of the treating physician. These agents will require a separate consent to be completed by the patient and physician. Suggested dose adjustments are in the table below.

Recently, the phase III randomized double-blind RATIFY study was completed and reported for patients with FLT3 mutated AML (Stone RM, et al. NEJM 2017) . 717 patients with FLT3 mutated AML were randomized to receive araC + daunorubicin with or without midostaurin. Midostaurin led to a significant improvement in survival (median 74.7 months for midostaurin vs. 25.6 for placebo; P=0.007). Based on this study, midostaurin was approved for the treatment of patients with FLT3 mutated AML in combination with chemotherapy, the first combination to show a survival benefit in several decades. This has now become part of the standard of care in the treatment of FLT3-mutated AML. Midostaurin has the additional benefit of targeting not only FLT3-ITD mutations, but also point mutations in the FLT3 kinase, such as D835 mutations. Therefore, AML patients with known FLT3-ITD or FLT3 kinase domain mutations will be allowed to receive midostaurin at the recommended dose of 50mg orally twice daily on days 6-19 during induction, and then on days 6-19 during consolidation. Dose adjustments and interruptions of the midostaurin are per standard of care and at the discretion of the treating physician. Suggested dose adjustments are in the table below.

# **Suggested Sorafenib Dosing Adjustments**

Dose Level	Sorafenib Dose and Schedule
0	400 mg PO Twice Daily
-1	400 mg PO Once Daily
-2	200mg PO Once Daily
-3	200mg PO Once Every Other Day

Suggested Midostaurin Dosing Adjustments		
Dose Level	Midostaurin Dose and Schedule	
0	50 mg PO Twice Daily	
-1	50mg PO Once Daily	
-2	50mg PO Every other Day	

Other FDA-approved FLT3 inhibitors or targeted therapies (e.g. IDH1 or IDH2 inhibitors) are allowed at the discretion of the treating physician and after discussion with the PI for patients harboring corresponding mutations.

Patients with the presence of the Philadelphia chromosome [translocation (9;22)] or the presence of the bcr-abl fusion gene (detected by PCR or FISH) – such as those with CML myeloid blast phase or 'Philadelphia-positive AML' – may benefit from concomitant therapy with an abl tyrosine kinase inhibitor (TKI). Several orally bioavailable TKIs have now been FDA approved for Philadelphia positive CML and their selection is based on patient tolerance, comorbidities, and abl kinase domain mutations. Patients with bcr-abl positive disease may receive concomitant therapy with an approved TKI, dosed orally,

continuously starting on day 1. The choice and dose will be per the discretion of the treating physician according to standard practice.

## 6. Central Nervous System (CNS) Prophylaxis and Treatment

All patients will receive at least one lumbar puncture during the first cycle of induction.

This is for diagnosis as well as for the application of prophylactic intrathecal chemotherapy (methotrexate 12 mg or cytarabine 100 mg).

The departmental standard of care for ALL patients is to administer 8 prophylactic intrathecal chemotherapy treatments during induction and consolidation. Methotrexate is alternated with cytarabine, and patients typically receive two treatments per cycle for the first four cycles.

For this protocol, giving more than one intrathecal treatment will be at the discretion of the managing physician. This degree of flexibility is warranted due to the heterogeneity of patients with MPAL. This will allow patients with predominantly myeloid disease to be spared unnecessary discomfort and risks. Patients that have predominantly lymphoid disease or others determined to be at high risk for developing CNS disease can receive up to 8 prophylactic intrathecal treatments.

## 7. Maintenance Therapy

Maintenance or continuation chemotherapy for up to 3 years is the standard of care for ALL patients. Furthermore, one of the larger experiences in MPAL gave all patients continuation therapy for 2.5 years. Other series have not included maintenance therapy. Therefore, maintenance therapy after the completion of consolidation will be at the discretion of the managing physician. Targeted therapy will continue during maintenance per the managing physician.

Maintenance can be given for up to 30 months as follows:

- Vincristine 2 mg (FLAT dose) IV over 15 30 minutes once monthly
- Prednisone 200 mg (FLAT dose) PO daily for 5 days every month
- Methotrexate 20 mg/m^2 PO given once weekly
- 6-Mercaptopurine 50 mg PO three times daily

Doses can be adjusted as clinically warranted at the discretion of the managing physician. In every day clinical practice, doses of methotrexate and 6-mercaptopurine are reduced for myelo- or hepato-toxicity. Vincristine is dose-reduced or omitted for clinically significant peripheral neuropathy. Corticosteroids are dose-reduced or omitted

in patients with active infectious issues. All dose adjustments in maintenance will be captured by research personnel for analysis.

## 8. Supportive care

Supportive measures such as prophylaxis for tumor lysis syndrome, anti-emetics, erythropoietin, analgesics, blood transfusions, antimicrobials and hematopoietic colony stimulating factors for treatment of cytopenias are permitted. The administration of anti-leukemia therapies is not permitted, except for hydroxyurea which is allowed for up to 7 days per cycle during cycles 1 – 3. The use of up to two doses of cytarabine (up to 3 g/m²) for emergency use up to 24 hours prior to start of study therapy is also permitted. As stated above, intrathecal chemotherapy is allowed for the prevention and treatment of CNS disease.

Patients may be concurrently enrolling in supportive care clinical trials. Other investigational agents that are used for treatment of other cancers will not be allowed.

Every effort will be made to adhere to the schedule of events and all protocol requirements. Variations in schedule of events and other protocol requirements that do not affect the rights and safety of the patient will not be considered as deviations. Such variations may include laboratory assessments completed outside of schedule, occasional missed required research samples such as PK or PD. All dose adjustments will be made according to the protocol unless otherwise specified.

#### VI. PRETREATMENT AND POST-TREATMENT EVALUATION

#### **Induction Treatment (Pre-treatment)**

- 1. CBC, differential, and platelet count.
- 2. Creatinine, bilirubin, ALT (SGPT) and/or AST (SGOT)
- 3. Echocardiogram or MUGA to assess left ventricular ejection fraction
- 4. Bone marrow aspirate and/or biopsy with cytogenetics (if bone marrow not done within 30 days or cytogenetics within 90 days. For patients with evidence of leukemia in the peripheral blood, the bone marrow may be omitted after discussion and approval with the principal investigator.)
- 5. Informed consent
- 6. Physical exam including vital signs and performance status
- 7. Concomitant medications and medical history
- 8. Pregnancy test (serum or urine)

#### Pretreatment Evaluation

Procedure	Comments	Schedule
Informed	Obtain standard informed consent approved by	Within 14 days of therapy
Consent	IRB	
Medical History	History of present illness, known allergies, prior cancer history as far as traceable, and past medical/ surgical history as far as relevant.	Within 14 days of therapy
Physical Examination	Vital signs (temperature, heart rate, respiratory rate, blood pressure) and performance status.	Within 14 days of therapy
Concomitant Medications	Document concomitant medications	Within 14 days of therapy
Hematology	CBC, differential, and platelet count (the differential may be omitted when the WBC is ≤ 500	Within 14 days of therapy

Procedure	Comments	Schedule
Biochemistry	Creatinine, total bilirubin, ALT (SGPT) and/or AST (SGOT)	Within 14 days of therapy
Bone marrow	Aspirate and/or biopsy To confirm complete remission	Within 30 days of therapy
	Cytogenetics	Within 90 days of therapy
Echo or Muga	Assessment of left ventricular ejection fraction	Within 14 days
Pregnancy test	Serum or urine, if female and of child-bearing potential only	Within 7 days of therapy

## **During induction therapy**

- 1. CBC, differential, and platelet count every 3-7 days (the differential may be omitted when the WBC is < 500.). Creatinine, bilirubin, ALT (SGPT) and/or AST (SGOT) once weekly.
- 2. Physical exam including vital signs (temperature, heart rate, respiratory rate, blood pressure) and performance status. Prior to each treatment course
- 3. Bone marrow aspirate and/or biopsy on day 28 +/- 7 days to confirm complete remission. Cytogenetics as clinically indicated.

# **During induction therapy**

Procedure	Comments	Schedule
Hematology	CBC, differential and platelet count	Every 3-7 days (the differential may be omitted when WBC is ≤500)
Biochemistry	Creatinine, bilirubin, ALT (SGPT) and/or AST (SGOT)	Once weekly
Physical Examination	Physical exam including vital signs (temperature, heart rate, respiratory rate, blood pressure) and performance status.	Prior to each treatment course

Bone marrow	Aspirate and/or biopsy to confirm complete remission. Cytogenetics as clinically indicated.	On day 28 +/- 7 days

## **During Post-Remission Therapy (Maintenance and consolidation)**

- 1. Physical exam including vital signs prior to each treatment course
- 2. CBC, differential, and platelet count prior to each post-CR course
- 3. Creatinine and bilirubin prior to each post-CR course
- 4. Bone marrow aspirates as indicated, cytogenetics as clinically indicated.

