#### Adverse effects:

- Hematologic: Myelosuppression, infections
- Hepato and Gastrointestinal: Nausea/vomiting, diarrhea, mucositis, stomatitis/pharyngitis, hyperbilirubinemia, increase of SGPT and/or SGOT, abdominal pain or cramping, peritonitis, pancreatitis, liver failure
- Dermatologic: Skin rash with blisters (particularly hand-foot syndrome), Steven-Johnson's syndrome, alopecia, conjonctivitis
- Systemic: Fatigue, asthenia, anorexia, lethargy, malaise, mental status changes/coma, alopecia
- Allergic reactions: (including fever, muscle aches, edema, dyspnea)
- Cardiology: Congestive heart failure

- Nephrology: Kidney failure
- Autoimmune reactions: (antiplatelet antibodies, erythema nodosum) and/or chemical imbalances in the blood.

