# IV. Eligibility Criteria

#### **Inclusion Criteria**

- 1. Sign an informed consent document
- 2. Age 18 >/= 18
- 3. Newly diagnosed or relapsed MPAL, which for this protocol, will be defined as follows:
- -Bone marrow result interpreted by the reading Pathologist (or tissue biopsy for cases of extramedullary disease) as: biphenotypic leukemia, bilineal leukemia, undifferentiated leukemia, mixed lineage leukemia, leukemia of ambiguous lineage, T/Myeloid leukemia, B/Myeloid leukemia, or other diagnosis indicating the presence of multiple lineages within the cell population.

Or

- -Immunophenotype consistent with WHO definition of MPAL
- 4. ECOG Performance Status of ≤ 3 at study entry.
- 5. Adequate organ function as outlined below (unless due to leukemia)
  - Serum creatinine ≤ 3 mg/dL
  - Total bilirubin ≤ 2.5 mg/dL
  - ALT (SGPT) and/or AST (SGOT) ≤ 3 x ULN or ≤ 5 x ULN if related to disease
- 6. Women of childbearing potential must have a negative serum or urine pregnancy test within 7 days. Women of childbearing potential and men must agree to use contraception at study entry and for the duration of active study treatment.
- Cardiac ejection fraction ≥ 40% (by either cardiac echo or MUGA scan).
   Documentation of recent (≤ 6 months from screening) outside reports is acceptable.
- 8. If newly diagnosed, prior therapy with hydrea and/or steroid and the use of a single or a two day dose of cytarabine (up to 3 g/m²), for emergency use up to 24 hours prior to start of study therapy is allowed.

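### Liver transaminases are not scheduled before consolidation cycles, so from about cycle 2 the pre-cycle toxicity check can be made without them

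*Combined protocol and SAP*

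**What the plan says.** The protocol treats transaminases differently before and after remission.

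- **Entry.** Inclusion criterion 5 (section IV) sets a limit: "ALT (SGPT) and/or AST (SGOT) ≤ 3 x ULN or ≤ 5 x ULN if related to disease". The pretreatment list and table in section VI include the same test, within 14 days of therapy.
- **Induction.** Section VI asks for "Creatinine, bilirubin, ALT (SGPT) and/or AST (SGOT) once weekly".
- **Post-remission.** Under the heading that covers both maintenance and consolidation, the chemistry line in section VI reads "Creatinine and bilirubin prior to each post-CR course". The other items are a physical examination, blood counts, and marrow and cytogenetics as indicated.

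Two rules in section V use toxicity grades during consolidation. Section V.3 says that before the next cycle "any clinically significant drug-related non-hematologic toxicity experienced by the patient must return to" grade 2 or below. Section V.4 allows doses in later consolidation cycles to be changed for clinically significant drug-related non-hematologic toxicity above grade 2. The organ-specific dose table in V.4 uses creatinine and bilirubin only.

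On exposure, section V.3 states "Patients in CR or CRi can continue with up to 6 consolidation cycles" and "Cycles may be repeated every 3 to 10 weeks". Each cycle includes clofarabine. Its adverse-effect list in section III.C contains "hyperbilirubinemia, increase of SGPT and/or SGOT", so the two liver findings are named separately.

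**The concern.** The condition for starting the next consolidation cycle is mandatory and is expressed as a toxicity grade. To grade a transaminase rise, the investigator needs the value. In consolidation the only liver test that the schedule guarantees is bilirubin, and clofarabine's own list treats raised bilirubin and raised transaminases as distinct effects. A patient with normal bilirubin and a drug-related transaminase rise above grade 2 could receive another cycle with every required test done and the rise unseen.

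Patient safety is the first thing at stake. The second is the data. Safety profile is a secondary endpoint (section VII), and section X has all adverse events recorded, but a rise that nobody tests for cannot be recorded. Hepatic findings after remission would then depend partly on which clinicians chose to order the test.

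**Working it through.** The question is one of consistency between the schedule and the rules it serves, so the check is mainly a side-by-side reading.

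**Step 1. Scheduled liver tests by phase (sections IV and VI).**

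| Phase | Bilirubin | ALT and/or AST |
|---|---|---|
| Entry and pretreatment | yes | yes |
| Induction | weekly | weekly |
| Post-remission (consolidation and maintenance) | before each course | not listed |

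The rest of the document was searched for a post-remission ALT or AST requirement. There is none in the supplied text.

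**Step 2. What each consolidation rule needs (sections V.3 and V.4).**

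| Rule | Information needed | Supplied by the schedule? |
|---|---|---|
| Organ-specific dose table | creatinine, bilirubin | yes |
| Condition for the next cycle (grade 2 or below) | grade of any clinically significant drug-related non-hematologic toxicity | not for transaminases |
| Dose change for toxicity above grade 2 | same class of toxicity | not for transaminases |

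The schedule matches the table exactly. It falls short only of the two broader, grade-based rules.

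**Step 3. How many checks are affected.** Consolidation has at most 6 cycles. Weekly induction chemistry may still give a recent value before cycle 1. That leaves 6 − 1 = 5 pre-cycle checks per patient, at most, with no scheduled transaminase behind them. With cycles 3 to 10 weeks apart, a patient who takes all 6 has 5 intervals between the start of cycle 1 and the start of cycle 6. That is 5 × 3 = 15 weeks to 5 × 10 = 50 weeks.

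**Step 4. Which events could be missed.** All of the following must hold: the rise is drug-related, above grade 2 and clinically significant, bilirubin is normal, and nobody orders the test for another reason. The documents give no rate for any of these, so no expected number can be calculated.

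**The case against.** The strongest reply is that the schedule is a coherent minimum. The dose table acts on two chemistry values, and the schedule orders those two. No post-remission threshold for ALT or AST exists, so a scheduled value would trigger no tabulated action. This stands, and it is why the dose table is not in question. It does not answer the two grade-based rules, which are wider than the table.

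A second reply is that the condition for the next cycle is a judgement about clinically significant toxicity and names no laboratory test. That also stands as a limit: a mild or unrelated rise is outside the rule. But the investigator cannot judge the significance of a value that was not measured.

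A third reply is that clinicians will test anyway. They may. An examination and bilirubin precede each course, and section V.8 does not treat laboratory work outside the schedule as a deviation. Section X refers to departmental reporting guidelines in an appendix that is not in the supplied text, so its content cannot be judged either way. None of the supplied text requires the test, whereas at entry and in induction the protocol did not leave it to habit.

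A reader might infer more than the documents support:

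- **That all 6 pre-cycle checks are uncovered.** Weekly induction testing may cover the first. How recent that value is depends on the gap before cycle 1, which the documents do not fix.
- **That multiplying cycles by expected responders measures the harm.** It would count blood samples, not missed events.
- **That maintenance has the same defect and needs a fixed testing interval.** Section V.7 describes everyday practice when it mentions reducing methotrexate and 6-mercaptopurine for liver toxicity, and leaves maintenance to the managing physician. It sets no protocol rule that the schedule fails to serve.
- **That the toxicity stopping rules are biased.** Sections 1.3 and 2.2 of the statistical considerations give no time window for counted events, so the documents do not settle whether a consolidation event would enter them.

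**Conclusion.** The point holds as a small, real mismatch between the post-remission schedule and the protocol's own toxicity rules for consolidation. From about cycle 2 onward, for up to 5 checks per patient, a drug-related transaminase rise above grade 2 with normal bilirubin could pass the required tests unseen and so be absent from the safety profile.

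This assumes that the schedule is followed as written, that induction testing gives a usable value before cycle 1, and that the patient takes all 6 cycles. Patients who take fewer have fewer affected checks. Consolidation is optional, so 5 is a ceiling.

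The number of missed events is unknown and may be zero. The primary endpoint and the tabulated dose adjustments are not affected. This is a cheap improvement and not a flaw that threatens the trial's conclusions.

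**What to change.** In the post-remission list in section VI, extend item 3 so that ALT and/or AST is measured together with creatinine and bilirubin before every post-remission course. The wording can follow the induction list, which already allows either enzyme.

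The test can be run on the sample already drawn for creatinine and bilirubin. The cost is one line of schedule text and one added laboratory value per course, at most 6 per patient in consolidation, with no extra visit or draw there. No sample size, endpoint or stopping boundary changes. The change will not detect a rise that appears and resolves between cycles, but it gives the investigator the value at the point where the decision is made.
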